4.1.2 Secondary Endpoints

All endpoints achieved within 30 day period after end of study drug treatment:

- Number of subjects with complete remission (defined as confirmed platelet response and absence of exacerbation)
- Number of (subjects with) exacerbations of TTP (defined as recurrent thrombocytopenia following a confirmed platelet response and requiring a re-initiation of daily PE treatment after ≥ 1 day but ≤ 30 days after the last daily PE) and time to first exacerbation of TTP
- Number of subjects relapsing of TTP (defined as *de novo* event of TTP that occurs later than 30 days after the last daily PE)
- Number of daily PE sessions, number of plasma units administered and number of days of daily PE
- Resolution of non-focal neurological symptoms as defined by neurocognitive function at complete remission, measured by a neurocognitive test battery
- Resolution or improvement (improvement of ≥ 1 grade in the CTCAE v4.0 scale) of TTP-related signs and symptoms as captured on physical examination and as adverse events, at complete remission and at end of the study drug treatment period (including tapering) (by number of unique subjects and by total number of AEs)
- Total mortality within the PE treatment period and within the subsequent study drug treatment period (including tapering)
- Incidence of PE treatment-related AEs, such as, but not restricted to: haemorrhage from catheter insertion, sepsis, catheter thrombosis, pneumothorax, fluid overload, hypoxia, hypotension, anaphylactoid reactions and TRALI

- Incidence and severity of ALX-0081 treatment-emergent AEs and relationship to study drug
- Development of ADA \leq 30 days post-last study drug treatment
- PK and PD profile

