## 6.1 Statistical and Analytical Issues

### 6.1.1 Statistical Methods

All data will be summarised by treatment group. In addition, where appropriate, a total overall group column will be included to summarise all subjects. Where appropriate, data will be summarised by treatment group and visit or whenever the assessment is done (e.g. the 1 and 3 week post-last day PE sampling may be done at the weekly visit, even if not at exactly 1 or 3 weeks).

All data will be listed and some selected variables will be tabulated or presented graphically, and will be noted where appropriate.

In summary and analysis tables of continuous variables, the minimum and maximum statistics will be presented to the same number of decimal places as the original data. The mean, median, quartiles, Least Squares mean (LS mean), and 95% Confidence Interval (CI) will be presented to one more decimal place than the original data, the standard deviation (SD) and standard error (SE) will be presented to two more decimal places than the original data. Standard descriptive statistics (number of subjects with data available [n], mean, SD, median, minimum and maximum) will be presented in summary tables. The LS mean, SE and 95% CI will be presented in the statistical analysis outputs as appropriate.

In summary tables of categorical variables, the number of non-missing observations and percentages will be presented. The denominator for each percentage will be the number of subjects within the population of interest [N] (unless otherwise specified).

All hypothesis testing will be 2-sided unless otherwise specified and carried out at the 5% significance level and designed to evaluate the superiority of ALX-0081 to placebo.

P-values will be rounded to three decimal places. P-values less than 0.001 will be reported as <0.001. P-values greater than 0.999 will be reported as >0.999.

Should any of the statistical methods (other than the primary endpoint analysis) proposed prove unsuitable during the final analysis, more appropriate methods will be used, and any changes documented in the CSR, including the rationale for use.

All statistical analysis will be performed using SAS® v9.2 or higher.

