### 6.3.2 Secondary Efficacy Variables

#### *Secondary Endpoints*

All endpoints achieved within 30 day period after end of study drug treatment:

- Number and percentage of subjects with complete remission (defined as confirmed platelet response and absence of exacerbation)
- Number and percentage of (subjects with) exacerbations of TTP (defined as recurrent thrombocytopenia following a confirmed platelet response and requiring a re-initiation of daily PE treatment after  $\geq 1$  day but  $\leq 30$  days after the last daily PE) and time to first exacerbation of TTP
- Number of daily PE sessions, number of total volume of plasma administered and number of days of daily PE
- Total mortality within the PE treatment period and within the subsequent study drug treatment period (including tapering)
- Number and percentage of subjects relapsing of TTP (defined as *de novo* event of TTP that occurs later than 30 days after the last daily PE)
- Number and percentage of subjects with platelets  $\geq 150,000/\mu$ L at day 30 of study drug administration (last treatment day visit) and one month follow-up time point
- Resolution or improvement (improvement of  $\geq 1$  grade in the CTCAE v4.0 scale) of TTP-related signs and symptoms as captured on physical examination and as adverse events, at complete remission and at end of the study drug treatment period (including tapering) (by number of unique subjects and by total number of AEs)
- Incidence of PE treatment-related AEs, such as, but not restricted to: haemorrhage from catheter insertion, sepsis, catheter thrombosis, pneumothorax, fluid overload, hypoxia, hypotension, anaphylactoid reactions and TRALI

---

This study has been statistically powered for the primary endpoint. No adjustment for multiplicity has been applied to the exploratory analysis for the secondary variables. All analysis will be performed on the ITT and PP populations and any p-values presented for secondary efficacy variables are purely exploratory (e.g. comparison of the number and percent of subjects with complete remission, exacerbations, relapse and daily PEs).

The number and percentage of subjects with complete remission at one month post first administration of study treatment, along with the exact binomial CI of the percentage will be presented by treatment group, overall and by ADAMTS13 activity  $< 5\%$  vs.  $\geq 5\%$  at baseline.

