The number and percentage of unique subjects with resolved or improved TTP-related signs and symptoms as captured on physical examination and as adverse events within the PE treatment period, within the ensuing 30 days and at the one month follow-up will be summarised by treatment and overall along with the exact binomial CI of the percentage. Improvement of physical examination is defined as progressing from an abnormal to a normal result for a particular system at a given time point. Resolution of physical examination is defined as having normal results for all systems at a given time point. Resolution of an adverse event is defined as having a stop date present and an outcome of either 'resolved' or 'resolved with sequelae' within the given period. Both physical examination systems and adverse events flagged as being related to TTP will be considered.

The number and percentage of deaths within the PE treatment period, within the ensuing 30 days (study treatment period) and within the period from the end of the study treatment period up to and including the one month follow-up will be presented for each treatment group and overall for the ITT population only. Each death will be categorised into one of the distinct periods identified above, such that the death is counted only once in the table.

The incidence of PE treatment-related AEs, such as, but not restricted to: hemorrhage from catheter insertion, sepsis, catheter thrombosis, pneumothorax, fluid overload, hypoxia, hypotension, anaphylactoid reactions and transfusion related acute lung injury (TRALI) will be summarised by system organ class, preferred term, treatment group and overall. The summary will be repeated for PE treatment-related SAEs for the ITT population only.

---

Frequency tables (with accompanying Chi-square p-values) will be made for the following characteristics: use of corticosteroids during daily PE, use of rituximab during daily PE and tapering. Use of corticosteroids will be determined by using the Concomitant Medications data (both PE related and not PE related) with ATC codes beginning with “H02” (systemic corticosteroids). Use of rituximab will be determined by using the Concomitant Medications data (both PE related and not PE related) with ATC code “L01XC” (coded term “RITUXIMAB”).

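### SAP 6.3.2 does not report the TTP signs-and-symptoms endpoint at the protocol's two time points, and its adverse-event rows count resolutions per period instead of status, without declaring the change

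*SAP*

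**What the plan says.** Protocol 4.1.2 sets the time points and the counting units: "at complete remission and at end of the study drug treatment period (including tapering) (by number of unique subjects and by total number of AEs"). The endpoint list that opens SAP 6.3.2 repeats the same two time points: "at complete remission and at end of the study drug treatment period (including tapering").

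The analysis paragraph later in SAP 6.3.2 says that unique subjects with resolved or improved signs "within the PE treatment period, within the ensuing 30 days and at the one month follow-up will be summarised", with exact binomial confidence intervals. It then gives three rules:

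- An AE is resolved if it has a stop date and "an outcome of either 'resolved' or 'resolved with sequelae' within the given period".
- Physical-examination resolution: "Resolution of physical examination is defined as having normal results for all systems at a given time point".
- Physical-examination improvement means "progressing from an abnormal to a normal result for a particular system at a given time point". The visit from which the change is measured is not stated.

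The default denominator is in SAP 6.1.1: "The denominator for each percentage will be the number of subjects within the population of interest [N] (unless otherwise specified"). SAP 6.1.5 discusses this endpoint, but the only change it declares is that CTCAE grade improvement cannot be derived for AEs. It says nothing about time points.

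**The concern.** The endpoint asks a status question: at a given moment, have the patient's TTP signs cleared or improved? For AEs the analysis text answers a different one: in which period did the resolution fall?

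Read literally, the AE rule treats a subject whose TTP-related AEs all stopped in the first days of PE as follows. At the end of study drug that subject is resolved. In the second row the subject has no stop date inside the period, so counts as zero, yet remains in the denominator. The second row ends at about the time study drug ends, so it is the row most likely to be read as the end-of-treatment result.

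The PE row has its own difficulty. Its length is the length of PE, which is expected to be shorter on an effective drug, so the two arms have unequal time in which a resolution can be counted.

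At stake is a named secondary endpoint whose protocol-defined result would not be reported, and a table in which one row can run against the arm that clears symptoms faster.

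**Working it through.** **1. Texts side by side**

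| Element | Protocol 4.1.2 and SAP endpoint list | SAP 6.3.2 analysis text |
|---|---|---|
| First anchor | Complete remission | PE treatment period |
| Second anchor | End of study drug | The following 30 days |
| Third anchor | None | One-month follow-up |
| Units | Unique subjects and total AEs | Unique subjects only |
| AE rule | Status at a time point | Resolved inside the period |
| Examination resolution | Status at a time point | Status at a time point |

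No row gives status at complete remission. The 30-day row approximates the end of study drug, but for AEs it is not a status.

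**2. Inputs for an illustration**

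The documents give no symptom-resolution rates and no figure for this endpoint. I borrow the platelet-response medians from SAP 6.1.4: 3.36 days (ALX-0081) and 6 days (placebo). As a check that these are the plan's working values, the Schoenfeld event count at one-sided 2.5% and 80% power is 4 × 7.849 / (ln 1.786)² = 93.4, so 94 events. Allowing 15% loss, 94 / 0.85 = 110.6, so 111 against the stated 110.

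My own assumptions are exponential times, one TTP-related AE per subject, PE ending 2 days after response, symptom resolution independent of platelet response within a subject, and study drug ending 30 days after PE.

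**3. Formulae**

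Let r = ln 2 / median response and k = ln 2 / median resolution.

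- Unresolved at the end of PE: U = exp(−2k) × r / (r + k)
- PE row: 1 − U
- Second row: U × (1 − exp(−30k))
- Status at end of study drug: the sum of the two rows

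**4. Scenario A: resolution is faster on the drug (medians 3.36 v 6 days)**

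- ALX-0081: r = k = 0.2063, U = 0.6619 / 2 = 0.331. PE row 66.9%; second row 0.331 × 0.9979 = 33.0%; status 99.9%.
- Placebo: r = k = 0.1155, U = 0.7937 / 2 = 0.397. PE row 60.3%; second row 0.397 × 0.9688 = 38.4%; status 98.8%.

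The second row runs against ALX-0081, the PE row favours it, and status slightly favours it.

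**5. Scenario B: equal resolution speed (median 6 days in both arms)**

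- ALX-0081: U = 0.7937 × 0.2063 / (0.2063 + 0.1155) = 0.509. PE row 49.1%; second row 49.3%; status 98.4%.
- Placebo: as above, 60.3%, 38.4% and 98.8%.

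Here the PE row runs against ALX-0081 only because its PE period is shorter, and the second row runs the other way.

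**6. Sensitivity to the assumptions**

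- PE fixed at 7 days in both arms, resolution medians 3.36 v 6: PE row 76.4% v 55.5%, second row 23.5% v 43.2%, status about 100% v 98.6%. For fixed PE of 5 to 16 days the second row ranges from 35.6% v 54.4% to 3.7% v 15.3%.
- PE lengths equal to the medians (3.36 v 6 days): PE row 50.0% v 50.0%, second row 49.9% v 48.4%. There is no reversal.
- Resolution coinciding with platelet response, PE stopping 2 days later: 100% and 0% in both arms. There is no reversal.

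**The case against.** A reader might infer that the SAP scores all TTP signs in exclusive windows, so that the table points the wrong way whenever the drug works. The documents do not support that.

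- Examination resolution is already a status. A patient who becomes normal during PE and stays normal still counts later. Only the AE rule is tied to a period.
- The SAP states single counting in distinct periods for deaths, not for resolutions. Whether an earlier AE resolution carries forward is left open, and a subject with several AEs can count in more than one row. The one-month follow-up is a visit, so how a period rule applies to AEs there is undefined.
- The rows offset each other. With one AE per subject they add up to the end-of-drug status, so a careful reader can recover it. Harm needs one row read alone.
- Independence of symptom resolution from platelet response is doubtful. Protocol 4.3 ties stopping daily PE to platelet count, neurological status and other clinical parameters.
- Timing is a legitimate interest: a secondary objective is shorter time to resolution of TTP symptoms.
- SAP 6.3.2 calls p-values on secondary variables purely exploratory, and no decision or error rate depends on this table.

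All of this stands, and it limits the size and the certainty of any distortion. It does not answer the textual point: the two anchors and the AE totals set in the protocol and in the SAP's own list are not what the analysis text produces, and the change is undeclared. A per-period count is also a weak way to show timing when the period length depends on treatment.

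**Conclusion.** The point holds in a limited form. Followed as written, SAP 6.3.2 does not yield the protocol-defined result: status at complete remission and the total-AE count are missing, end-of-drug status for AEs is replaced by a per-period count, and SAP 6.1.5 is silent on this.

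The possible distortion concerns the AE component only, and only under the literal reading without carry-forward. Its size is illustrative: a second-row deficit of about 5 percentage points for the faster arm in scenario A, beside a PE-row advantage of about 7 points and near-ceiling status in both arms. It rests on borrowed platelet medians, a 2-day lag and independence. Some assumption sets give larger reversals and others none, so the documents do not support a claim that the table will be biased against ALX-0081.

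Severity is minor to moderate: a reporting inconsistency in an exploratory secondary endpoint that is cheap to remove.

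**What to change.** In the SAP 6.3.2 analysis text, replace the periods with cumulative status at two dates: complete remission and last study drug dose.

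- **AEs:** resolved if flagged TTP-related, with a resolved outcome and a stop date on or before that date.
- **Physical examination:** TTP-flagged systems normal at the last examination on or before that date. State the reference visit for improvement.
- **Units:** unique subjects and total number of AEs.
- **Date of complete remission:** define it. SAP section 3 makes it depend on absence of exacerbation and gives no date. One option is the date of confirmed platelet response in subjects without exacerbation.
- **Non-remitters and deaths:** count as not resolved, and say so.
- **One-month follow-up:** keep as an additional status time point.
- **SAP 6.1.5:** list any period-based summary that is retained as a declared change. If timing is of interest, label such a summary as timing and not as the endpoint.

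The cost is SAP wording and reprogramming of one table. AE stop dates and outcomes, examination dates and dosing dates are already collected, so no new data are needed.

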### **6.3.3 Glasgow Coma Score**

The Glasgow Coma Score will be determined using the Glasgow Coma Scale (original scale), which is a neurological scale that measures the conscious state of the subject. The best eye opening, verbal and motor responses will be scored according to the scale, and the separate scores added up to obtain the final score, ranging from 3 to 15. Scores will be summarised within each system (eye opening, verbal and motor) and final score by treatment group and visit for the ITT and PP populations.

### **6.3.4 Neurocognitive Battery**

The neurocognitive battery, consisting of the CNTB and two manually-administered, pencil and paper tests (Category Fluency and Letter Fluency), administered at the baseline and during the treatment phase. The CNTB has 6 modules: word list learning and selective reminding (WLL/SR), choice reaction time (CRT), visual memory (VMEM), simple reaction time (SRT), working memory (WMEM), and word list learning and delayed recall (WLL/DR).

The average summary score for CNTB, the total score and the change from baseline total score for Category Fluency and Letter Fluency (Trials 1, 2 and 3 respectively) will be

---

summarised by treatment group and visit using summary statistics for continuous variables for the ITT population.

### 6.3.5 Longer-Term Variables

[REDACTED]

- [REDACTED]

[REDACTED]

[REDACTED]

[REDACTED]

### 6.3.6 Other exploratory analyses

[REDACTED]

[REDACTED]

---

## 6.4 Safety Analysis

Analysis of all safety data will be performed on the safety analysis population.

### 6.4.1 Adverse Events

All AEs will be classified using the Medical Dictionary for Regulatory Activities (MedDRA) coding dictionary version 15.0 or higher.

Events will be classified as *treatment-emergent* if they started on or after date of first dose of study drug. Treatment-emergent adverse events are therefore a subset of all adverse events. If an event start date is partial, then the start month, year or stop date will be used to determine if the event is treatment-emergent. If the classification of the AE cannot be determined from the data available, then the event will be considered treatment-emergent.

The following presentations will be produced by treatment group and overall:

*Treatment-emergent events:*

- A general summary table reporting the number of events and the number and percentage of subjects with events will be presented by treatment group. The following categories will be included in this general summary table:
  - The number of subjects having any adverse event.
  - The number of subjects having at least one treatment-emergent adverse event.
  - The number of subjects having at least one TTP-related treatment-emergent adverse event.
  - The number of subjects having at least one PE-related treatment-emergent adverse event.

- 
- The number of subjects having at least one drug-related treatment-emergent adverse event (defined as related or possibly related to study treatment).
  - The number of subjects having at least one treatment-emergent adverse event leading to discontinuation of study drug (defined as having study treatment action taken recorded as “study drug discontinued”).
  - The number of subjects having at least one treatment-emergent adverse event leading to interruption of study drug (defined as having study treatment action taken recorded as “study drug interrupted”).
  - The number of subjects having at least one treatment-emergent adverse event leading to interruption or discontinuation of study drug (defined as having study treatment action taken recorded as either “study drug interrupted” or “study drug discontinued”).
  - The number of subjects having treatment-emergent adverse events with death as outcome.
  - The number of subjects having at least one serious adverse event.
  - The number of subjects having at least one serious treatment-emergent adverse event.
  - The number of subjects having at least one serious treatment-emergent drug-related adverse event.
- 
- Treatment-emergent AEs and SAEs will be summarised by system organ class and preferred term. The number of events and the number and percentage of subjects having each event will be presented.
  - Treatment-emergent AEs and SAEs will be summarised by system organ class, preferred term and severity. The number of events and the number and percentage of subjects having each event will be presented for the maximum severity reported for each event. The maximum severity per preferred term will be evaluated for each subject and the resulting dataset will be used to present the summary. Any missing severity will be left as missing and categorised as such.

- 
- Treatment-emergent AEs and SAEs will be summarised by system organ class, preferred term and relationship to study drug. The number of events and the number and percentage of subjects having each event will be presented for the most conservative relationship to study drug reported for each event. For example, if a subject has both a related and a possibly related event in the same preferred term, the related event will be taken for summary. The most conservative relationship per preferred term will be evaluated for each subject and the resulting dataset will be used to present the summary. Any missing relationship will be left as missing and categorised as such.
  - Treatment-emergent AEs that lead to discontinuation of study drug will be summarised by system organ class and preferred term. The number of events and the number and percentage of subjects having each event will be presented.
  - Treatment-emergent AEs that lead to interruption of study drug will be summarised by system organ class and preferred term. The number of events and the number and percentage of subjects having each event will be presented.
  - Treatment-emergent AEs that lead to interruption or discontinuation of study drug will be summarised by system organ class and preferred term. The number of events and the number and percentage of subjects having each event will be presented.

Note: If a subject records multiple AEs with the same preferred term, these shall be summarised once within the count for n (%) of subjects, yet each event will be counted within the number of reports n\* of each AE. AEs that have grade changes reported in the CRF shall be counted once, at the maximum severity reported.

*All adverse events:*

All recorded adverse events will be listed.

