9. SAFETY DEFINITIONS AND REPORTING REQUIREMENTS

9.1 Adverse Events

9.1.1 Definitions of Adverse Events

An AE is “any untoward medical occurrence in a patient or clinical investigation subject administered a study drug and which does not necessarily have a causal relationship with this treatment”. An AE can therefore be any unfavourable and unintended sign (including an abnormal laboratory finding), symptom, or disease temporally associated with the use of a study drug, whether or not related to the study drug.

A treatment-emergent AE is any AE temporarily associated with the use of a study drug, whether or not considered related to the study drug.

AEs include:

- Exacerbation of a pre-existing disease
- Increase in frequency or intensity of a pre-existing episodic disease or medical condition
- Disease or medical condition detected or diagnosed after study drug administration even though it may have been present prior to the start of the study
- Continuous persistent disease or symptoms present at baseline that worsen following the start of the study
- Lack of efficacy in the acute treatment of a life-threatening disease
- Events considered by the Investigator to be related to study-mandated procedures
- Abnormal assessments, e.g., ECG, vital signs or physical examination findings, must be reported as AEs if they represent a clinically significant finding that was not present at baseline or worsened during the course of the study
- Laboratory test abnormalities must be reported as AEs if they represent a clinically significant finding, symptomatic or not, which was not present at baseline or worsened during the course of the study

AEs do not include:

- Medical or surgical procedure, e.g., surgery, endoscopy, tooth extraction, transfusion. However, the event leading to the procedure is an AE. If this event is serious, the procedure must be described in the SAE narrative
- Pre-existing disease or medical condition that does not worsen
- Situations in which an adverse change did not occur, e.g., hospitalisations for cosmetic elective surgery or for social and/or convenience reasons, or elective

hospitalisation for observation in order to facilitate the follow-up when practical and logistical circumstances exist.

- Overdose of either study drug or concomitant medication without any signs or symptoms. However, overdose must be mentioned in the Study Drug Log

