9.1.6 Reporting of Adverse Events

All AEs occurring after the start of the study must be recorded until end of follow-up (1y), or until subject withdrawal. Subjects entry into the study is defined as the time at which informed consent is obtained. All subsequent AEs, irrespective of whether no drug, study drug or placebo was administered, must be recorded on specific AE pages of the respective CRF, regardless of whether or not they are considered to be study drug related. AEs occurring from study drug initiation until 30 days post study drug discontinuation (inclusive) are defined as treatment emergent.

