9.2.2.3 After Study Drug Discontinuation

All SAEs occurring within and including 30 days after study drug discontinuation must be recorded and reported on an SAE form and on the AE pages of the respective CRF. These SAEs are defined as treatment emergent.

SAEs occurring after 30 days post last administration of study drug are reported until end of follow-up (1y), or until subject withdrawal (as per section 5.4.2).

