10.3 Evaluation of Safety and Tolerability Parameters

All safety parameters (physical examination, vital signs, bleeding, ECG-parameter, biochemistry/haematology and ADA evaluations, concomitant medications (including PE characteristics) and AEs) will be summarised descriptively by treatment. Quantitative variables will be described by n, mean, standard deviation, median, minimum and maximum. Qualitative variables will be described by frequency tables containing counts and percentages. Additionally, shift tables will be provided for the safety laboratory parameters (within, below or above normal range) from pre-study to post-dose.

The AEs will be coded according to MedDRA and tabulated by system organ class, preferred term and lower level term. An AE will be referred to by the treatment and time point after which it occurred, i.e. any AE occurring before the dosing will be counted as a baseline AE and will be considered as a treatment-emergent AE only if the severity or relation to drug changes.

No formal statistical testing will be performed on the safety data.

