#### **6.4.7 Immunogenicity**

ADA in serum will be determined by an immuno assay and processed at GLP Pharma. Immunogenicity testing will be performed on the timepoints indicated in [Appendix I](#). A separate immunogenicity report will be prepared and presented as an Appendix to the Final Clinical Study Report.

The number and percentage of subjects who developed anti-drug antibodies (ADA)  $\leq$  30 days post-last study drug treatment will be presented by treatment group and overall.

The number and percentage of subjects who developed ADA  $>$  30 days post-last study drug treatment will be presented by treatment group and overall.

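### SAP 6.4.1 gives treatment-emergent AEs no end date, while the protocol closes the window 30 days after study drug; the change is not declared and could affect the end-of-study AE/SAE tables

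*SAP*

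**What the plan says.** - **SAP 6.4.1** makes AEs treatment-emergent "if they started on or after date of first dose of study drug". A rule for partial start dates follows, and unresolved cases count as treatment-emergent. No end date is given there or in the definitions in SAP Section 3.
- **Protocol 9.1.6** has both limits: "AEs occurring from study drug initiation until 30 days post study drug discontinuation (inclusive) are defined as treatment emergent". The same section sets a much longer recording period: "All AEs occurring after the start of the study must be recorded until end of follow-up (1y), or until subject withdrawal".
- **Protocol 9.2.2.3** applies the same 30-day limit to SAEs ("These SAEs are defined as treatment emergent") and deals with later SAEs in a separate sentence.
- **Protocol 4.1.2** lists the incidence and severity of treatment-emergent AEs among the secondary endpoints, under the lead-in "All endpoints achieved within 30 day period after end of study drug treatment".
- **SAP 6.1.5** declares three changes from the protocol: one on CTCAE improvement and two on the neurocognitive battery. The treatment-emergent window is not among them.
- **SAP 6.6** plans a first analysis on the 1-month follow-up data and a second at the end of the study, with outputs that include data to one year. **Protocol 12.10** places the 12-month results in an addendum to the study report.

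**The concern.** The label treatment-emergent is meant to separate events that could reflect exposure from events that arise long after it. With no end date, every AE that starts after the first dose keeps the label for as long as the subject is followed.

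A relapse shows how this could happen. Protocol 5.4.2 and 7.2 do not allow study drug to be restarted for a relapse, and Table 14 requires daily AE recording during the plasma exchange that treats it. An AE from a relapse months after the last dose would be treatment-emergent under SAP 6.4.1 and outside the window under protocol 9.1.6.

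At stake is the meaning of the descriptive AE and SAE summaries. The same table title could cover one window in the main report and another in the addendum, and neither document would tell the reader so.

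**Working it through.** No design figure depends on this point, so the check sets the two definitions side by side and compares window lengths. These are days of observation, not counts of events.

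**Inputs**
- T = days from first to last dose, at most 90 (protocol 7.2).
- Protocol window ends at T + 30 (protocol 9.1.6 and 9.2.2.3).
- Follow-up runs 12 months from last study drug (protocol synopsis and 8.1.3), taken as 365 days, with a 12-month visit window of ±15 days.
- 1-month visit: ±3 days (SAP 1.3).

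**Protocol's own limit.** At the treatment maximum the protocol window is 90 + 30 = 120 days from first dose.

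**End of study, follow-up counted from last dose**

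Excess of the SAP window = (T + 365) − (T + 30) = 335 days. With the visit window it is 350 − 30 = 320 to 380 − 30 = 350 days.

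| T (days) | Basis | Protocol window | SAP window | Share of SAP window outside protocol window |
|---|---|---|---|---|
| 90 | protocol maximum | 120 | 455 | 335/455 = 74% |
| 46 | assumed: 16 days of exchange + 30 | 76 | 411 | 335/411 = 82% |
| 36 | assumed: 6 days of exchange + 30 | 66 | 401 | 335/401 = 84% |

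The last two rows are illustrations. Protocol 2.5.2 gives an average of about 16 exchanges to remission. The 6 days are the control median time-to-response from the sample size section, used here as a stand-in for days of exchange, which they are not.

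**End of study, follow-up counted as in protocol 4.4**

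That section starts the year at remission or after 90 days of treatment, whichever comes first. With remission on day R, no later than the last dose:

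Excess = (R + 365) − (T + 30) = 335 − (T − R).

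- No remission before day 90, T = 90: still 335 days.
- Assumed R = 6 and T = 36: 371 − 66 = 305 days.
- T − R cannot exceed 90, so the excess is at least 335 − 90 = 245 days for a subject followed to a nominal 12-month visit.

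**First analysis**

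If AEs are cut at each subject's 1-month visit, the excess is at most (30 + 3) − 30 = 3 days, and zero if the visit falls on day 30 or earlier. Neither document states this cut for AEs. Recruitment is expected to take 30 months and the main report follows the last subject's 1-month visit (protocol 12.10). Without a cut, subjects enrolled early could bring up to a full year of follow-up AEs into the main tables.

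**Separate erratum.** SAP Section 3 converts °F to °C by multiplying by 9, dividing by 5 and adding 32. For 98.6 °F that gives 98.6 × 9/5 + 32 = 209.5. The correct result is (98.6 − 32) × 5/9 = 37.0 °C. SAP 6.4.3 relies on this conversion.

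**The case against.** The protocol is not uniform. Its general definition in 9.1.1 ("A treatment-emergent AE is any AE temporarily associated with the use of a study drug") gives no number of days. Its statistical section, 10.3, says that "any AE occurring before the dosing will be counted as a baseline AE" and sets no upper limit either. So the SAP can be said to follow one part of the protocol while departing from another. That is fair, but silence in two places does not cancel an explicit 30-day limit stated once for AEs and again for SAEs.

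The consequence is also partly inferred. SAP 6.6 promises outputs with one-year data but does not say that the 6.4.1 tables will be rerun, and protocol 12.10 describes the addendum as concerned with disease outcome. For the first analysis, SAP 1.2, SAP 6.6 and protocol 12.10 all point to the 1-month follow-up. This part of the objection stands: the end-of-study effect is possible, not certain.

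The SAP does split ADA, with separate counts for development up to and later than "30 days post-last study drug treatment will be presented by treatment group and overall". That shows the split is workable. It does not prove that the AE omission was an oversight, because the ADA bullet in protocol 4.1.2 carries its own 30-day limit and the AE bullet does not.

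The damage is limited. Safety data are not formally tested (protocol 10.3), all AEs are listed, and deaths and bleeding have their own tables. Tables of AEs leading to interruption or discontinuation are essentially unaffected, since an AE that starts more than 30 days after the last dose cannot cause either.

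A reader might infer more than the documents support:
- *That the SAP loses pre-dose AEs that worsen on drug.* Protocol 9.1.3 closes such an AE and opens a new record, so the start-date rule largely picks it up.
- *That SAP 6.1.5 and 6.4.1 contradict each other on grade changes.* The first concerns CTCAE grade and the second maximum severity; protocol 9.1.4 treats these as separate classifications.
- *That the open window favours one arm.* Both arms share the follow-up schedule, so the likely effect is extra off-drug events in both.

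**Conclusion.** The mismatch is established from the text: the SAP window has no end, the protocol window ends 30 days after discontinuation, and the change is not declared. It should be corrected before database lock, but it touches no efficacy result and no formal test.

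If the 6.4.1 tables are rerun at the end of the study, the window is about 335 days too long (320 to 350) for a subject followed 12 months from last dose. It is shorter, though at least about 245 days, if the year is counted as in protocol 4.4. Withdrawal would shorten it further.

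The main report is affected by about 0 to 3 days, on the assumption of a per-subject cut at the 1-month visit. The claim that its tables are materially misclassified is not supported, although nothing written rules it out. The number of events that would change class cannot be derived from the documents.

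**What to change.** In SAP 6.4.1:
- define treatment-emergent as onset from first study drug administration to 30 days after last study drug, inclusive;
- apply the existing partial-date rule to the end boundary as well;
- tabulate later AEs and SAEs separately as follow-up events;
- state the per-subject AE cut for the first analysis.

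If a wider window is intended, declare and justify it in SAP 6.1.5 instead.

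The cost is SAP wording and programming from AE onset and last-dose dates. No new data collection and no protocol amendment are needed, and later events remain reported in their own table.

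As a separate correction, SAP Section 3 should read °C = (°F − 32) × 5/9. This adds no weight to the point above.
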